8.4.3.3 Expectedness

The Windtree Medical Monitor or designee will be responsible for determining whether an AE is expected or unexpected. An AE will be considered unexpected if the nature, severity, or frequency of the event is not consistent with the risk information previously described for the study intervention (ie, as per the Investigator's Brochure).

8.4.4 Time Period and Frequency for Event Assessment and Follow-Up

The occurrence of an AE or SAE may come to the attention of study personnel during the study, or upon review by a study monitor.

All AEs including local and systemic reactions not meeting the criteria for SAEs will be captured on the appropriate eCRF. All AEs occurring while on study must be documented appropriately regardless of relationship. All AEs will be followed to adequate resolution.

Any medical condition that is present at the time that the participant is screened will be considered as baseline and not reported as an AE. However, if the study participant's condition deteriorates at any time during the study, it will be recorded as an AE.

Changes in the severity of an AE will be documented to allow an assessment of the duration of the event at each level of severity to be performed. AEs characterized as intermittent require documentation of onset and duration of each episode.

The site will record all reportable events with start dates occurring any time after informed consent is obtained until 7 days after the last day of study participation or Day 30 (whichever occurs first). Events will be followed for outcome information until resolution or stabilization, or for 30 days after study participation. When possible, information collection should continue for subjects that withdraw or discontinue treatment early.

8.4.5 Adverse Event Reporting

All AEs are to be assessed in all subjects throughout Day 30 (from enrollment to study withdrawal or completion) and documented in the study eCRF. Each AE should be reported spontaneously or in response to general, non-directed discussion with the attending nurse or physician (eg, "has there been any change in subject status since the last assessment period?"). For each AE, the investigator should obtain all information required to complete the AE page of the eCRF, in accordance with eCRF completion guidelines (provided separately by Windtree).

All AEs, regardless of seriousness, severity, or relationship to study participation, must be recorded (using medical terminology) in the source document and on the AE page of the eCRF. Whenever possible, diagnoses should be given when signs and symptoms are due to a common etiology.

All AEs must be followed until resolution or until a stable clinical end-point is reached, or for at least 30 days after the subject's last day in the study if an AE is ongoing at the time the subject completes the study.

Documentation of AEs in the eCRF must include the following parameters; (1) duration (time of onset and resolution), (2) severity or grade, (3) outcome, (4) action taken, and (5) relationship to study drug. AEs will be coded using the Medical Dictionary for Regulatory Activities (MedDRA).

8.4.6 Serious Adverse Event Reporting

When an investigator-trained designee becomes aware of an SAE, Windtree must be notified as soon as possible (and no later than 24 hours after the event has occurred) by telephone, regardless of the relationship (or lack thereof) of the SAE to study participation.

SAEs should be reported to Windtree's reporting line. When reporting SAEs, the following information should be provided:

- 1. Study identifier
- 2. Study center
- 3. Subject number
- 4. A description of the event
- 5. Date of onset
- 6. Current status

- 7. Clarification on whether infusion therapy was discontinued
- 8. The reason why the event is classified as serious
- 9. The Investigator's assessment of the association between the event and study participation

All reports of SAEs must be followed up within 24 hours (or sooner at the request of the medical monitor) by the completion of the SAE form and signature by the person who completed the form and the PI.

Safety report distribution is the responsibility of Windtree or designee (ie, CRO), which coordinates distribution of safety reports to applicable regulatory authorities and ECs. Finalized safety reports are distributed by one or more individuals, "Responsible Team," within a department that has responsibility to coordinate the distribution/submission activities, either directly or via a Local Submitting Party on behalf of Windtree.

The Responsible Team receives finalized safety reports (eg, CIOMS-I form/MedWatch 3500A/ E2B file/DSUR/SUSAR Listing) and coordinates distribution to all applicable regulatory

authorities and ECs. Distribution will be done in accordance with project-specific documents, regulatory requirements, other applicable reference sources, and applicable Windtree or designee safety procedural documents.

In addition, Windtree coordinates translation when required for safety reporting. Windtree also coordinates transcription (eg, manual transfer of information from one reporting format to another) when required. Project specific information is used to identify appropriate recipients. Quality checks will be permed on the distribution documents and recipient information for completeness and accuracy prior to distribution.

The names, telephone, and fax numbers of the individuals who should be contacted regarding safety issues are listed below.

FOR QUESTIONS, PLEASE CONTACT THE MEDICAL MONITOR:

[name] (Medical Monitor)

WhatsApp: [name] Office: [contact]

8.4.7 Reporting Events to Subjects

Occurrences of AEs or SAEs that impact the risk to subjects in the study may result in a change in the informed consent form. Subjects who have not yet completed the study must be reconsented with the amended informed consent form.

8.4.8 Events of Special Interest

Air leaks (eg, pneumothorax, pneumomediastinum) will be considered AEs of special interest. Air leaks should be reported using the reporting line within 24 hours of becoming aware of the air leak.

8.4.9 Reporting of Pregnancy

The use of lucinactant in women of childbearing potential not using contraceptive measures should be avoided; women of childbearing potential must have a negative pregnancy test (β -hCG) recorded prior to administration of lucinactant and at the end of the study. Men and premenopausal women will be required to use double-barrier methods of birth control for 30 days following discharge from the hospital. Failure to commit to double-barrier methods will be a reason for screen failure.

If a woman becomes pregnant during the study, the pregnancy will be followed until delivery or termination, and pertinent information about the pregnancy will be collected (eg, AEs, concomitant medications).

9 STATISTICAL CONSIDERATIONS

9.1 Statistical Hypothesis

As this is an open-label study with no comparison group, no hypotheses will be used for this study.

9.2 Sample Size Determination

The objective of this safety pilot study is to determine if lyophilized lucinactant administration is safe and tolerable, and to assess the impact on oxygenation for those patients suffering with COVID-19. As a result, no formal sample size calculation was performed but instead enroll a sufficient number of subjects to provide evidence that liquid lucinactant can be safely delivered as an intratracheal bolus.

Thus, up to 30 subjects (out of approximately 90 screened) will be enrolled.

9.3 Populations for Analyses

Populations of all enrolled subjects who received any treatment (modified intent-to-treat [mITT]) will be evaluated for safety and efficacy.

9.4 Statistical Analyses

9.4.1 General Approach

All efficacy and safety parameters will be evaluated using summary statistics. For continuous variables, n, mean, standard deviation, median, min, and max will be presented; for discrete variables, frequency and percent will be presented.

9.4.2 Analysis of the Primary Efficacy Endpoint(s)

The primary endpoint is the change from baseline in OI through 12 hours post dosing. OI is define as $(FiO_2 \times P_{aw} \times 100)/PaO_2$. OI will be summarized using mean, standard deviation (SD), median, minimum, and maximum.

9.4.3 Analysis of the Secondary Endpoint(s)

9.4.3.1 Through 24 Hours Post Treatment

OI, FiO₂, PaO₂, SpO₂, PaCO₂, P/F and S/F ratios, change in plateau pressure and PIP measured on the ventilator, VI, and lung compliance will be summarized as change from baseline at each time point measured using mean, SD, median, minimum, and maximum.

9.4.3.2 Through 30 Days

Daily lung compliance on ventilator, ventilator free days, days in the ICU, days in the hospital, organ failure free days, and all-cause mortality will be summarized as was done for the primary endpoint.

All deaths will be summarized using frequency and percent, overall and by type of death (respiratory or not respiratory) and included as part of the assessment of safety. Also, the deaths will be listed by subject and narratives for each death will be included. In this study, the secondary endpoint of ventilator-free days (VFD) is a mortality adjusted assessment. This issue will be dealt with in more detail in preparation for the next study.

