- Safety and Tolerability of reconstituted lyophilized lucinactant given as a bolus to patients with COVID-19.
- Change from baseline in OI at 12 hours post initiation of dosing. OI is defined as P_{aw}×FiO₂×100/PaO₂.

Secondary Efficacy Variables:

- Change from baseline through 24 hours post dosing initiation:
 - \circ FiO_{2:}
 - o PaO₂;
 - o SpO₂;
 - o OI;
 - o PaCO₂;
 - o ETCO₂;
 - P/F and or S/F ratios, defined as PaO₂ or SpO₂ divided by FiO₂;
 - Plateau pressure and peak inspiratory pressure (PIP) measured on the ventilator;
 - Ventilation Index (VI). VI is defined as $[RR \times (PIP PEEP) \times PaCO_2]/1000$;
 - o Lung compliance;
 - o Pressure-volume loops if ventilator technology permits.
- Through 30 days:
 - o Daily lung compliance (static) on ventilator;
 - Ventilator-free days;
 - o Days in the intensive care unit (ICU);
 - Days in the hospital;
 - o Incidence of all-cause mortality;
 - o Organ failure free days.

Safety Variables:

- All-cause mortality;
- Peri-dosing adverse events (desaturation, bradycardia, ET reflux, hypotension)
- AEs and serious AEs (SAEs). SAEs that are ongoing at Day 30 will be followed for an additional 30 days;
- Air leaks as AEs of special interest;
- Assessments of vital signs.

Study Population:

The study population will be comprised of adults 18-75 (inclusive) who are positive for SARS-CoV-2, are exhibiting symptoms of severe COVID-19 infection, who are intubated and are receiving mechanical ventilation in a critical care environment.

The objective of the pilot safety study is to evaluate the safety and feasibility of lucinactant administration in COVID-19 patients. A small number of patients should be sufficient to provide evidence that liquid lucinactant can be safely delivered as an intratracheal bolus. A total of up to 30 study subjects will be enrolled (see "Treatment Group" section).

Description of Sites:

Approximately 15 study sites in the United States and Argentina.

Description of Study Intervention:

Reconstituted lyophilized lucinactant will be given at a dose of 160 ml (30 mg TPL/ml), delivered as a liquid in the trachea through the endotracheal tube. Lyophilized lucinactant has the following four active ingredients:

- sinapultide (a synthetic peptide), consisting of amino acid residues lysine (K) and leucine (L), according to the sequence KLLLKLLLKLLLKLLLKKLLLK (KL₄);
- dipalmitoyl-phosphatidylcholine (DPPC);
- palmitoyloleoyl-phosphatidylglycerol, sodium salt (POPG, Na); and

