1.2 Schedule of Activities (SOA)

		Primary Phase Through Day 30		
Measurement/Procedure	Screening	Treatment Period (Day 1)	Post-Treatment Period (Days 2-5)	Final Period (Days 6 to 30)
Informed consent	X			
Inclusion/exclusion Criteria	X			
Demographics	X			
Medical history	X			
Physical examination	X			
Enrollment		X		
Study treatment administration		X		
Vital signs	X	X	X^2	X
ABG (PaO ₂ , PaCO ₂ , pH)		X^1	X	X
FiO ₂ , SpO ₂ , P _{aw} , EtCO ₂		X^1	X	X
Ventilator parameters (rate, peak and plateau pressure, lung compliance)		X^2	X^2	
Respiratory support parameters	X	X	X	X
Pressure volume loops		X^3		
AEs/SAEs		X	X	X ⁵
Concomitant medications	X	X	X	X
Final Visit/Discharge				X^4

Note: Day 1 for all subjects is the day of enrollment.

Time 0 (study treatment), 1, 2, 4, 8, 12, 18, 24 hours after treatment

 $^{^{2}}$ $\,$ Recorded every 12 hours at 08:00 and 20:00 through Day 5.

³ Recorded every 2 hours through 24 hours.

⁴ Occurs at Day 30, withdrawal from the study, or death (whichever occurs first).

⁵ AEs ongoing at Day 30 will be followed for an additional 30 days or until stop date/time (whichever occurs first).

TABLE OF CONTENTS

TITLE PAGE	I
STATEMENT OF COMPLIANCE	3
PROTOCOL AGREEMENT	4
1 PROTOCOL 02-CL-2001A	5
1.1 Summary	5
1.2 Schedule of Activities (SOA)	14
TABLE OF CONTENTS	15
2 INTRODUCTION	19
2.1 Study Rationale	19
2.2 Background	19

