8.2.2 Vital signs

Blood pressure, heart rate, and body temperature will be measured every 12 ± 1.0 hours until Day 5 and at Day 30. Systolic and diastolic blood pressure should be measured using either an arterial line or a manual sphygmomanometer with the patient in a supine or semi-supine position.

Weight will be measured at baseline and at Day 30.

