10.1.4 Future Use of Stored Specimens and Data

No specimens will be taken for this study.

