- 4.9.1 Efficacy Analysis – Plateau Pressure and Peak Inspiratory Pressure (PIP) through 24 Hours – Modified Intent-to-Treat Population
- 4.9.2 Efficacy Analysis – Plateau Pressure and Peak Inspiratory Pressure (PIP) through 24 Hours – Intent-to-Treat Population
- 4.10.1 Efficacy Analysis – Ventilation Index (VI) through 24 Hours – Modified Intent-to-Treat Population
- 4.10.2 Efficacy Analysis – Ventilation Index (VI) through 24 Hours – Intent-to-Treat Population
- 4.11.1 Efficacy Analysis – Lung Compliance (Dynamic) through 24 Hours – Modified Intent-to-Treat Population
- 4.11.2 Efficacy Analysis – Lung Compliance (Dynamic) through 24 Hours – Intent-to-Treat Population
- 4.12.1 Efficacy Analysis – Daily Lung Compliance (Static) on Ventilator – Modified Intent-to-Treat Population
- 4.12.2 Efficacy Analysis – Daily Lung Compliance (Static) on Ventilator – Intent-to-Treat Population
- 4.13.1 Efficacy Analysis – Ventilator Free Days – Modified Intent-to-Treat Population
- 4.13.2 Efficacy Analysis – Ventilator Free Days – Intent-to-Treat Population
- 4.14.1 Efficacy Analysis – Days in the Intensive Care Unit (ICU) – Modified Intent-to-Treat Population
- 4.14.2 Efficacy Analysis – Days in the Intensive Care Unit (ICU) – Intent-to-Treat Population
- 4.15.1 Efficacy Analysis – Days in the Hospital – Modified Intent-to-Treat Population
- 4.15.2 Efficacy Analysis – Days in the Hospital – Intent-to-Treat Population
- 4.16.1 Efficacy Analysis – Incidence of All-Cause Mortality – Modified Intent-to-Treat Population
- 4.16.2 Efficacy Analysis – Incidence of All-Cause Mortality – Intent-to-Treat Population
- 4.17.1 Efficacy Analysis – Organ Failure Free Days – Modified Intent-to-Treat Population
- 4.17.2 Efficacy Analysis – Organ Failure Free Days – Intent-to-Treat Population
- 5.1.1 Peri-Dosing Adverse Events – Initial Dose – Safety Population
- 5.1.2 Peri-Dosing Adverse Events – Repeat Doses – Safety Population
- 5.2 Air Leaks – Safety Population
- 5.3.1 Treatment-Emergent Adverse Events by System Organ Class and Preferred Term – Safety Population
- 5.3.2 Treatment-Emergent Adverse Events by System Organ Class and Preferred Term by Severity – Safety Population
- 5.3.3 Treatment-Emergent Adverse Events by System Organ Class and Preferred Term by Relationship to Study Treatment – Safety Population
- 5.3.4 Treatment-Emergent Adverse Events by System Organ Class and Preferred Term by Severity and Relationship to Study Treatment – Safety Population

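### Organ failure free days through Day 30 has no definition and no matching data collection, so the planned tables would rest on incomplete ascertainment

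*Protocol*

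**What the plan says.** The endpoint stands in the 30-day list of secondary efficacy variables in Protocol 1.1 ("Organ failure free days"), in Protocol 3, and in the SAP Executive Summary and SAP 1.2.3. For the analysis, Protocol 9.4.3.2 states that "days in the hospital, organ failure free days, and all-cause mortality will be summarized as was done for the primary endpoint"; SAP 4.2.2 repeats this. SAP 10 lists "Efficacy Analysis – Organ Failure Free Days – Modified Intent-to-Treat Population" as Table 4.17.1, with an ITT counterpart as Table 4.17.2. Protocol 9.4.3.2 calls ventilator-free days mortality adjusted but says nothing similar for organ failure free days.

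On data collection:

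- The schedules in Protocol 1.2 and SAP 2.2.4 cover vital signs, blood gases, oxygenation, ventilator and respiratory support parameters, pressure-volume loops, adverse events and concomitant medication.
- Protocol 8.2.2: "Blood pressure, heart rate, and body temperature will be measured every" 12 hours up to Day 5, then once at Day 30. Protocol 8.2.1 gives blood gases a similar span: the first 24 hours, daily to Day 5, then Day 30.
- Protocol 8.2.3 records respiratory support up to Day 30, or to discharge if earlier.
- Protocol 6.5 names vasopressors among the medications to be recorded up to the final assessment. Protocol 8.3.1.1 ends medication recording earlier if the subject is discharged, transferred or dies.
- Protocol 8.4.5 collects adverse events through Day 30 by spontaneous report or non-directed questioning. Under Protocol 8.4.4, a condition "present at the time that the participant is screened will be considered as baseline and not reported as an AE", unless it worsens.

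**The concern.** A count of failure-free days needs three things: a definition of failure for each organ, a daily source that shows whether the definition is met, and a rule for days on which the subject is dead or out of sight. The plan supplies none of these for this endpoint, yet commits to two summary tables. Whoever programs the tables would have to choose the organs, thresholds, sources and death rule after the data are in. This is what SAP 1 says the SAP exists to prevent.

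The likely fallback is adverse event records. They depend on someone volunteering the event, and they leave out stable organ dysfunction already present at screening. That can occur: Protocol 5.1 admits subjects on vasopressor support, and Protocol 5.2 sets the renal exclusion only at creatinine clearance below 30 mL/min. SAP 1.2 also says that the efficacy estimate will be used to size later studies, so a number of unknown meaning could be carried forward.

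**Working it through.** The plan gives no figure for this endpoint to reproduce. The check traces the endpoint to its data sources and counts the days each source covers. The documents name no organs; the six used here (lung, circulation, kidney, liver, coagulation, brain) are an assumption.

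**Step 1. Scheduled coverage of Days 1 to 30.**

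- Kidney, liver, coagulation, brain: no laboratory value or score is scheduled after enrollment in either schedule or in Protocol 8.2 and 8.3, so 0 of 30 days. Creatinine clearance, neutrophil and white cell counts, and troponin appear only in the eligibility criteria.
- Blood pressure and blood gases: Days 1 to 5 plus Day 30, so 5 + 1 = 6 of 30 days. The gap is 30 − 6 = 24 days, and 24/30 = 80%.
- Type of respiratory support: up to 30 of 30 days, ending at discharge.
- Vasopressor use: up to 30 of 30 days as a medication record, ending at discharge or transfer under Protocol 8.3.1.1.
- Adverse events: up to 30 of 30 days for every organ, but non-directed and subject to the screening-baseline rule.

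Daily data independent of adverse event reporting therefore exist for at most two of the six assumed organs, lung and circulation, and only through records of support. If lung failure counts, every subject starts in failure, because intubation is an entry criterion, and the measure largely repeats ventilator-free days.

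**Step 2. Effect of scoring unrecorded failure as free.** Let p be the share of subjects with non-pulmonary organ failure, L its length in days within the window, and u the share of those days that goes unrecorded. The mean is then too high by p × L × u. None of these inputs is in the documents; the assumed ranges are p = 0.20 to 0.40, L = 5 to 10 days and u = 0.25 to 1.00.

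- Lowest: 0.20 × 5 × 0.25 = 0.25 days.
- Middle: 0.40 × 5 × 0.50 = 1.0 day.
- Highest: 0.40 × 10 × 1.00 = 4.0 days.

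**Step 3. Effect of the missing death rule.** Suppose one rule scores each death as 0 and another credits failure-free days before death. Each day credited per death moves the mean by the proportion who die. Protocol 2.4.1 gives 14% in one earlier lucinactant group and in standard of care at Day 28; Protocol 2.2.1 gives up to 40% for ARDS. Assuming mortality here lies in that range, the shift is 0.14 to 0.40 day per credited day. Among 30 subjects that is 0.14 × 30 = 4.2 to 0.40 × 30 = 12 deaths.

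**The case against.** The best defence is that the tables can be produced, and a reader who infers otherwise goes too far. Adverse events carry onset, resolution and severity (Protocol 8.4.5), may be abnormal laboratory findings (Protocol 8.4.1), and include any new clinically relevant finding (Protocol 7.1). With vasopressor dates and the respiratory support record, a table could be assembled. That stands; the weakness is ascertainment, not impossibility.

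Three other strong readings also fail:

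- A reader might take "No specimens will be taken for this study" in Protocol 10.1.4 as proof that no organ-function values exist. That section concerns stored specimens. The protocol takes blood gases and pregnancy tests, and Protocol 10.1.9.2 lists laboratory reports as source documents.
- A reader might say that four organs are never observed in the 30 days. Adverse event assessment is scheduled throughout, and SAP 5.4.2 plans a final physical examination by body system. What is absent is scheduled laboratory or score data.
- A reader might call the result biased upward outright. No passage says that an unobserved day counts as free, and SAP 4.3, which uses available data without imputation, leaves it open. The upward bias is conditional on that scoring.

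It is also fair that the exclusions remove some dysfunction at entry, including severe renal impairment and multiple-dose vasopressors, and that worsening must be recorded. A definition based on organ support could be largely computed while subjects are in hospital. The eCRF and study manual are not among the documents, so an organ-failure form cannot be ruled out, although neither document mentions one. Finally, the study is descriptive and no stated decision rule uses this endpoint.

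**Conclusion.** The point holds as a mismatch between a named endpoint and the planned data. Organ failure free days has no definition and no rule for death, discharge or transfer. Kidney, liver, coagulation and brain have no scheduled laboratory or score data after enrollment, and blood pressure and blood gases leave 80% of the window uncovered. A table from the remaining sources would be under-ascertained. It would overstate failure-free days if unrecorded failure is scored as free, by roughly 0.25 to 4.0 days in the mean under assumed inputs.

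The absence from the protocol and SAP is certain. The size rests on the six-organ list and the assumed frequencies, durations and recording rates. No hypothesis test is affected, so this should be corrected but does not threaten the main safety and oxygenation summaries.

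**What to change.** Delete organ failure free days from Protocol 1.1, 3 and 9.4.3.2, from the SAP Executive Summary and SAP 1.2.3 endpoint lists, from SAP 4.2.2, and from the table list (Tables 4.17.1 and 4.17.2). Alternatively, relabel it as adverse-event-reported organ failure and present incidence only, not a count of days.

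If a circulatory outcome is wanted, days alive and free of vasopressors through Day 30 can optionally be reported from the existing medication dates, with these rules written down:

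- deaths by Day 30 score 0;
- days after discharge home alive count as free;
- subjects transferred while still hospitalised are unobserved from transfer, reported separately and not counted as free.

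The two statements of when medication recording ends (Protocol 6.5 and 8.3.1.1) would then need to agree. Ventilator-free days already covers the respiratory part.

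The cost is wording in both documents and a removed or retitled pair of tables, with no new procedure for deletion or relabelling. The vasopressor option also requires that discharge home can be told apart from transfer. The downside is that the trial no longer claims a multi-organ outcome.
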